2.2.2 Dose Rationale

Mirabegron 25 mg, which may be increased to 50 mg based on individual efficacy and tolerability, is the approved dose in the treatment of overactive bladder in the United States and Canada [Mirabegron US Package Insert, 2012 and Myrbetriq Canadian Monograph, March 2013]. The dosing regimen of mirabegron 25 mg increased to mirabegron 50 mg after 4 weeks of treatment is intended to reflect a pragmatic and clinically plausible regimen. The treatment effect size at Week 4 in the phase 3a program approaches the maximum treatment response for incontinence and micturition.

The study design employs an optional dose increase from 25 mg mirabegron to 50 mg mirabegron at either Week 4 (Visit 4) or Week 8 (Visit 5) based on the individual subject efficacy, tolerability, and Investigator discretion. Once a patient has increased dose, they will remain on that dose for the remainder of the study unless for safety reasons that require discontinuation of study drug.

2.3 Variables

2.3.1 Primary Variable

The co-primary efficacy endpoints are:

- Change from baseline to the end of treatment in mean number of micturitions/24 hour based on a 3-day micturition diary.
- Change from baseline to end of treatment in mean number of incontinence episodes/24 hour based on a 3-day micturition diary.

2.3.2 Secondary Variables

Secondary endpoints are:

- Change from baseline to the end of treatment in mean volume voided per micturition.
- Change from baseline to the end of treatment in symptom bother and total health related quality of life scores as assessed by OAB-q questionnaire.
- Change from baseline to the end of treatment in Patient Perception of Bladder Condition (PPBC).

2.3.3 Other Variables

Other efficacy variables are the change from Baseline (Week 0) to End of Treatment (Week 12) in:

- Mean number of urgency episodes (grade 3 and/or 4)/24 hour
- Mean number of urgency incontinence episodes/24 hour
- Mean level of urgency
- Mean number of nocturia episodes/24 hour
- Subscale score from OAB-q scores
- TS-VAS
- University of Alabama, Birmingham - Life Space Assessment (UAB-LSA)
- Responder analysis as defined by $\geq 50\%$ reduction from baseline in mean number of incontinence episodes/24 hours from baseline or zero incontinence episodes post-baseline.

3 STUDY POPULATION

3.1 Selection of Study Population

This study will enroll male and female subjects greater than or equal to 65 years old who have symptoms of OAB. Eight hundred subjects will be randomized (1:1) to either mirabegron or placebo, stratified by age (< 75 years, ≥ 75 years).

3.2 Inclusion Criteria

Subject is eligible for the study if all of the following apply:

Inclusion Criteria assessed at Visit 1 (Screening):

1. Institutional Review Board (IRB)/Independent Ethics Committee (IEC)-approved written Informed Consent and privacy language as per national regulations (e.g., HIPAA Authorization for U.S. sites) must be obtained from the subject or legally authorized representative prior to any study-related procedures (including withdrawal of prohibited medication, if applicable).
2. Male or female subject greater than or equal to 65 years of age.
3. Subject is willing and able to complete the micturition diary and questionnaires correctly.
4. Subject has symptoms of OAB (urinary frequency and urgency with incontinence) for greater than or equal to 3 months prior to Screening.
5. Subject agrees not to participate in another interventional study from the time of screening until the final study visit.

Inclusion Criteria assessed after placebo run-in period at Visit 3 (Baseline):

1. Subject continues to meet all criteria of Visit 1.
2. Subjects must experience at least one incontinence episode based on the 3-day micturition diary.
3. Subject must experience at least 3 episodes of urgency (grade 3 or 4) based on the 3-day micturition diary.

4. Subject must experience an average of greater than or equal to 8 micturitions/day based on the 3-day micturition diary.

Waivers to the inclusion criteria will NOT be allowed.

3.3 Exclusion Criteria

Exclusion Criteria assessed at Visit 1 (Screening):

1. Subject has ongoing symptoms suggestive of bladder outlet obstruction (BOO) or history of BOO that is not currently well controlled.
2. Subject has Post-Void Residual Volume (PVR) greater than 150 mL.
3. Subject has neurogenic bladder or neurological dysfunction or injury which could affect the lower urinary tract or nerve supply.
4. Subject has significant stress incontinence or mixed stress/urgency incontinence where stress is the predominant factor as determined by the Investigator (for female subjects confirmed by a cough provocation test). Subjects with a history of stress incontinence that is currently treated (e.g., remote history of surgery for stress incontinence) may be included as long as they pass cough provocation test.
5. Subject has an indwelling catheter or practices intermittent self-catheterization.
6. Subject has evidence of Urinary Tract Infection (UTI). Urine cultures and sensitivity will be performed for positive leukocytes, or nitrites, or turbidity, or at the investigator's discretion, and will be confirmed with a culture greater than 100,000 cfu/mL. If a subject has a UTI, at Screening (Visit 1) the subject can be rescreened after successful treatment of the UTI (confirmed by a laboratory result of negative urine culture).
7. Subject has a chronic inflammatory condition such as interstitial cystitis, bladder stones, previous pelvic radiation therapy, or previous or current malignant disease of the pelvic organs (i.e., within the confines of the pelvis including the bladder and rectum in both sexes and the uterus, ovaries and fallopian tubes in females; organs of the lower gastrointestinal tract are not necessarily considered pelvic organs as the distal ascending colon, the full transverse colon and proximal portion of the descending colon are in the abdomen).
8. Subject resides in a nursing home.
9. Subject is likely to enter a hospital or nursing home due to a medical instability within the next 6 months in the opinion of the Investigator.
10. Subject has received intravesical injection in the past 12 months with botulinum toxin, resiniferatoxin, or capsaicin.
11. Subject has received electro-stimulation therapy for OAB (e.g., sacral nerve stimulation or PTNS).
12. Subject began or has changed a bladder training program or pelvic floor exercises less than 30 days prior to Screening.
13. Subject has moderate or severe hepatic impairment defined as Child-Pugh Class B or C.
14. Subject has severe renal impairment defined as estimated creatinine clearance less than 29 mL/min determined by Estimated Glomerular Filtration Rate (eGFR, Cockcroft-Gault, or MDRD formulae). A subject with end stage renal disease or undergoing dialysis is also not a candidate for the study.

15. Subject has severe uncontrolled hypertension, which is defined as a sitting systolic blood pressure greater than or equal to 180 mmHg and/or diastolic blood pressure greater than or equal to 110 mmHg.
16. Subject has evidence of QT prolongation on ECG defined as QTc greater than 450 msec for males, QTc greater than 470 msec for females or a known history of QT prolongation.
17. Subject has a clinically significant ECG abnormality, as determined by the Investigator.
18. Subject has AST or ALT greater than 2x upper limit of normal (ULN), or γ -GT greater than 3x ULN and considered clinically significant by the Investigator.
19. Subject has a hypersensitivity to any components of mirabegron, other β -AR agonists, or any of the inactive ingredients.
20. Subject has any clinically significant condition, which in the opinion of the Investigator makes the subject unsuitable for study participation.
21. Subject has been treated with an experimental device within 28 days or received an investigational agent within 28 days or 5 half-lives, whichever is longer, prior to Screening.
22. Subject has a concurrent malignancy or history of any malignancy (within the past 5 years), except non-metastatic basal or squamous cell carcinoma of the skin that has been treated successfully.
23. Subjects with current history of alcohol and/or drug abuse.
24. Subject is using prohibited medications which cannot be stopped safely during the period defined in Appendix 1.
25. Subject has stopped, started or changed the dose of a restricted medication (defined in Appendix 1) within the last 30 days prior to Screening.
26. Subject is involved in the conduct of the study as an employee of the Astellas group, third party associated with the study, or the study site team.
27. Subject has previously received mirabegron.

Exclusion Criteria assessed after placebo run-in period at Visit 3 (Baseline):

1. Subject fulfills any exclusion criteria of Visit 1 (subject does not need to repeat screening assessments [PVR, cough provocation test, chemistry/hematology/urinalysis]).
2. Subject was non-compliant during 2-week placebo run-in period, defined as taking less than 80% and greater than 120% of study medication.
3. Subject has any systolic blood pressure measurement \geq 180 mmHg or diastolic blood pressure measurement \geq 110 in the 3-day diary or during the baseline visit.

Waivers to the exclusion criteria will NOT be allowed.

4 TREATMENTS

4.1 Identification of Investigational Product(s)

4.1.1 Test Drug

Mirabegron will be supplied as 25 mg and 50 mg OCAS (Oral Controlled Absorption System) modified release tablets.

Mirabegron OCAS tablets contain the following excipients: [REDACTED]

The mirabegron OCAS tablets are packaged in 30 cc round wide mouth white HDPE bottles sealed with white child resistant polypropylene caps. Each bottle contains 30 tablets and must be stored at room temperature, 25°C (77°F); excursions permitted to 15°-30°C (59°-86°F).

All investigational materials must be kept in a secure area inaccessible to unauthorized individuals.

4.1.2 Placebo

The placebo to match (PTM) mirabegron OCAS tablets contain [REDACTED]

The mirabegron PTM tablets are packaged in a 30 cc round wide mouth white HDPE bottles sealed with white child resistant polypropylene caps. Each bottle contains 30 tablets. The HDPE bottles must be stored at room temperature, 25°C (77°F); excursions permitted to 15°-30°C (59°-86°F).

4.2 Packaging and Labeling

All medication used in this study will be prepared, packaged, and labeled under the responsibility of a qualified person(s) at Astellas U.S. Technologies, Inc. (AUST) in accordance with AUST Standard Operating Procedures (SOPs), Good Manufacturing Practice (GMP) guidelines, ICH GCP guidelines, and applicable local laws/regulations.

4.3 Study Drug Handling

Current ICH GCP Guidelines require the Investigator to ensure that study drug deliveries from the Sponsor are received by a responsible person designated by the Investigator (e.g. pharmacist, study coordinator), and

- that such deliveries are recorded
- that study drug is handled and stored safely and properly
- that study drug is only dispensed to study subjects in accordance with the protocol
- that any unused study drug is returned to the Sponsor or standard procedures for the alternative disposition of unused study drug are followed and authorized by Astellas.

Drug inventory and accountability records for the study drugs will be kept by the Investigator/ pharmacist and in the IRT system. Study drug accountability throughout the study must be documented. The following guidelines are therefore pertinent:

- The Investigator agrees not to supply study drugs to any persons except the subjects in this study.
- The Investigator/pharmacist will keep the study drugs in a locked and secure storage facility under controlled storage conditions, accessible only to those authorized by the Investigator to dispense these test drugs.
- A study drug inventory will be maintained by the Investigator/pharmacist. The inventory will include details of material received, a clear record of when they were dispensed and to which subject, and when and how much was returned by each subject.
- At the conclusion or termination of this study, the Investigator/pharmacist agrees to conduct a final drug supply inventory and to record the results of this inventory on the Drug Accountability Record. It must be possible to reconcile delivery records with those of used and returned medication. Any discrepancies must be accounted for. Appropriate forms of deliveries and returns must be signed by the person responsible.

4.4 Blinding

4.4.1 Blinding Method

This is a randomized, double-blind, parallel group study. Subjects will be assigned to a treatment group in the order which they meet the criteria for randomization. After the completion of the 2-week placebo run-in period, subjects will be randomized to either 25 mg mirabegron or placebo for 12 weeks of treatment. Subjects will receive their allocated treatment according to a computer-generated randomization schedule prepared by the Sponsor or designee prior to the start of the study. The subject, Investigator and Sponsor will not be aware of the treatment regimen.

4.4.2 Confirmation of the Indistinguishability of the Study Drugs

Mirabegron and mirabegron PTM tablets will be used in this study. The mirabegron PTM will be identical in size, color and appearance to the mirabegron 25 mg and mirabegron 50 mg tablets.

4.4.3 Retention of the Assignment Schedule and Procedures for Treatment Code Breaking

Study drug treatment may be revealed only for reasons relating to the subject's safety and when critical therapeutic decisions are contingent on knowing the assigned study drug.

Withdrawal of a subject from the study (refer to Section 6.1) is not a sufficient reason to break the study blind. Any decision to break the blind must be discussed with the Astellas Study Physician (refer to Section II for contact information).

If the blind is broken for a subject, the reason is to be documented as a written entry in the source document. Key information will be recorded at the time when the blind is broken. This includes the date the blind was broken, the reason, the person who requested the breaking of the blind, the name of the person who broke the blind, and the name of the Astellas representative contacted.

4.4.4 Breaking the Treatment Code for Emergency

Breaking the treatment code, or unblinding of an individual subject's treatment assignment, may be done only for reasons relating to subject safety or when critical therapeutic decisions are contingent upon knowing the blinded study drug assignment. As noted in Section 4.4.3, the reason to break the blind must be discussed with the Astellas Study Physician prior to unblinding.

After receiving authorization for unblinding from the Sponsor, the Investigator will utilize the interactive response technology (IRT) system to unblind. Unblinding through the interactive system may only be done by the designated individuals at the site.

If it becomes necessary to break the code during the study, the date, time and reason will be recorded in the subject's Electronic Case Report Forms (eCRF).

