4.4.5 Breaking the Treatment Code by the Sponsor

The Sponsor may break the treatment code for subjects who experience a Suspected Unexpected Serious Adverse Reaction (SUSAR), in order to determine if the individual case or a group of cases requires expedited regulatory reporting. Individual Emergency Code will be provided to the limited staff who are empowered to break the codes for all SUSAR cases for reporting purposes.

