4.5 Assignment and Allocation

After a subject signs informed consent, a subject number will be assigned. To obtain a subject number, the Investigator or designee will utilize a web or phone-based Interactive Response Technology (IRT), available seven days a week and 24 hours a day.

Subjects who meet all the inclusion and none of the exclusion criteria will enter a 2-week placebo run-in period (Visit 2). At Visit 3 (Baseline), subjects will be randomly assigned to receive 25 mg mirabegron or placebo using a 1:1 randomization schedule.

To obtain the randomized treatment, the Investigator or designee will utilize a web or phone-based IRT, available seven days a week and 24 hours a day. After submitting certain information about the eligible subject, the randomized drug assignment will be provided by the IRT. Study drug assignment will remain blinded to all staff. Study drug will be packaged in bottles. Each study drug bottle will be preprinted with a Medication ID number. The Medication ID number assigned to the subject will be noted in the electronic case report form (eCRF) for study drug.

Once a subject number is assigned, if the corresponding subject does not receive study drug, the subject number will not be used again.

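### Protocol 4.4.4 makes prior Sponsor authorization a condition of Investigator unblinding even in an emergency, and the available text gives no exception or fallback

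*Protocol*

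**What the plan says.** Protocol 4.4.4 is the section for emergencies. It says that breaking the code "may be done only for reasons relating to subject safety or when critical therapeutic decisions are contingent upon knowing the blinded study drug assignment". It then sets two steps before the code can be seen. First, "the reason to break the blind must be discussed with the Astellas Study Physician prior to unblinding". Second, "After receiving authorization for unblinding from the Sponsor, the Investigator will utilize the interactive response technology (IRT) system to unblind". It also limits who may act: "Unblinding through the interactive system may only be done by the designated individuals at the site".

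Protocol 4.4.3, the general section, says: "Any decision to break the blind must be discussed with the Astellas Study Physician". It refers sites to Section II for contact details. The record it asks for includes the date, the reason, who requested and who performed the code break, and "the name of the Astellas representative contacted".

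The SAP has no emergency procedure. Section 3.3 says that assignment stays blinded to all staff. Table 3 in 5.2.1 lists unblinding (criterion 10) among the possible reasons for exclusion from the per protocol set.

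**The concern.** Section 4.4.4 accepts that some treatment decisions turn on knowing the assignment, and that subject safety can justify a code break. For exactly those cases it makes the information wait on two actions by someone away from the bedside: a conversation, then an authorization. Neither has a time limit, and nothing says what the site should do if the study physician cannot be reached.

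What is at stake is access to the code by the team responsible for the subject. The population is aged 65 and over, and Protocol 1.3.1 lists increased heart rate and increased blood pressure among the important potential risks. An acute event in which the treating team wants the assignment is therefore foreseeable, even if uncommon.

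**Working it through.** No arithmetic applies: the point depends on no rate, effect size, alpha or sample size. The check is whether any text relaxes the two steps in 4.4.4.

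1. **Is the condition mandatory, and does it cover emergencies?** Yes. Both steps stand in the emergency section itself, the discussion is worded as a must, and authorization is placed before use of the IRT.

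2. **Does 4.4.3 relax it?** No. It extends the discussion requirement to every decision to break the blind. It does not say that the discussion must come first, although 4.4.4 cites it for that.

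3. **Is there another route to the code?** Only one, in 4.4.5: "Individual Emergency Code will be provided to the limited staff who are empowered to break the codes for all SUSAR cases for reporting purposes". That is a Sponsor-side route for regulatory reporting. It gives the treating Investigator nothing.

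4. **Do the overdose or SAE sections give an exception?** No. Protocol 5.1.4, 5.5.5 and 5.5.9 cover supportive care, monitoring, reporting times and product information. None mentions unblinding.

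5. **Does the SAP give one?** No. Sections 3.3 and 5.2.1 contain only the statements noted above.

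6. **Is there a general clause that would help?** Yes, one. Protocol 8.1.6 bars Investigators from deviating from the protocol except where needed to remove an immediate hazard to subjects. An Investigator could rely on it, but the code break would then be a deviation, and nothing in 4.4.4 points there.

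7. **What do the documents say about IRT hours?** Section 4.5 describes the IRT as "available seven days a week and 24 hours a day", but for obtaining a subject number and the randomized treatment. The hours of the unblinding function are not stated.

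8. **Are the grounds for unblinding the same in both sections?** No. Section 4.4.3 joins subject safety and critical therapeutic decisions with *and*; 4.4.4 joins them with *or*. Read literally, the first requires both grounds and the second either one.

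Steps 1 to 5 establish the condition with no specific exception. Step 6 is a partial relief. Steps 7 and 8 are loose ends in the same sections.

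**The case against.** The strongest reply has four parts.

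- **Contacts may be covered elsewhere.** Section II is not in the text available. Attachment 1 shows that it carries a 24-hour contact line for SAEs and an entry for the study physician. This stands: backup contacts may exist, and the absence of a fallback can be asserted only for the available text. A contact would shorten the wait; the authorization condition would remain.

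- **Section 8.1.6 already protects the subject.** This stands in part. It shows that the protocol accepts the principle, which is a reason to state it in 4.4.4 rather than leave sites to justify a deviation afterwards.

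- **Most emergency care does not need the code.** Protocol 5.1.4 calls for symptomatic and supportive treatment of overdose, and 6.1 lets the Investigator end a subject's involvement when the clinical condition warrants it. This stands: what may wait is the code, not care in general. The documents name no specific emergency decision that depends on the assignment, although 4.4.4 provides for such decisions.

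- **Prior review protects the blind.** It does, but in a small number of cases, and the documentation rules and PPS criterion 10 would still capture each one.

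A reader might also infer more than the text supports:

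- *That the authorization rule is the only source of delay because the IRT is always open.* Section 4.5 gives those hours for other functions, and the limit to designated site staff could also cause delay.
- *That the Sponsor holds a veto, or that the IRT is locked until the Sponsor releases it.* No text describes a refusal, and the rule as written is procedural.
- *That QT prolongation or overdose shows an immediate need for the code.* Protocol 1.3.1 ties the QT risk to supratherapeutic doses or high-risk populations, and 5.1.4 names no treatment that depends on the code.

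**Conclusion.** The point holds in limited form. Protocol 4.4.4, read with 4.4.3, makes prior discussion and prior Sponsor authorization conditions of Investigator unblinding even in an emergency. The available text has no exception beyond the general clause in 8.1.6.

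The size cannot be quantified. The documents give neither a rate of emergency unblinding nor a response time, so any count of affected subjects or length of delay would be guesswork. Cases should be few, and no effect on the primary analysis is claimed.

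The conclusion assumes that sites follow 4.4.4 as written and that Section II holds contact details rather than an exception to the authorization step. If Section II does contain an exception, the remaining task is to put it in 4.4.4, where a site would look. This is a cheap improvement to subject safety, not a flaw that threatens the trial's results.

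**What to change.** Amend 4.4.3 and 4.4.4 together:

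- When a subject's emergency care depends on the assignment, designated site staff may unblind through the IRT on the Investigator's judgment, without waiting for Sponsor authorization.
- Contact with the study physician beforehand is encouraged when time allows, but is not a condition.
- The Sponsor is told promptly afterwards, without the assignment going to anyone who does not need it.
- The existing record of each code break is kept. The two sections should also agree on where it is held, since 4.4.3 puts the reason in the source document and 4.4.4 puts date, time and reason in the eCRF.
- The *and* in 4.4.3 and the *or* in 4.4.4 are reconciled, so that sites have one test.

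Also confirm that the IRT unblinding function is open to sites at all hours, and that the designated staff arrangement works out of hours.

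The cost is a short protocol edit and a check with the IRT provider. Whether any system setting must change is not known from the documents. The downside is that a few subjects may be unblinded without prior Sponsor review. The SAP needs no change, because criterion 10 in 5.2.1 already covers unblinded subjects.
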